7.2. Randomization, Blinding, and Unblinding

7.2.1. Stage 1

Stage 1 of the trial is open-label, and all patients will receive setmelanotide.

7.2.2. Stage 2

Patients who are eligible to enter Stage 2 of the trial will be randomized in a blinded manner on Day 112 (Stage 2 Entry Visit) in a 2:1 ratio to receive either setmelanotide (2) or placebo (1). The randomization schedule will be generated by the Sponsor or its designee, and trial personnel will use a web-based interactive response technology (IRT) system to obtain the randomization number for each eligible patient.

Stage 2 of this trial is double-blinded. The patient, Investigator, and Sponsor will be blinded to trial treatment.

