7.7. Concomitant Medications

Medication that is considered necessary for the patient's safety and wellbeing may be given during the trial at the discretion of the treating physician after discussion with the Medical Monitor.

All concomitant medications should be kept at a stable dose throughout the course of the trial unless a dose change is necessary due to an AE.

Any medication or vaccine (including over-the-counter or prescription medicines, vitamins, and/or herbal supplements) that the patient is receiving at the time of enrollment or receives during the trial must be recorded along with:

- Reason for use
- Dates of administration including start and end dates
- Dosage information including dose and frequency

GLP-1 receptor agonists and anti-obesity medications may be used as long as:

- the regimen and/or dose has been stable for at least 3 months prior to randomization
- the patient has not experienced weight loss $\geq 2\%$ during the previous 3 months, AND
- the patient intends to keep the regimen and/or dose stable throughout the course of the trial.

The Sponsor should be contacted if there are any questions regarding concomitant or prior therapy.

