	
[REDACTED]
 
[REDACTED]
	
[REDACTED]
 
[REDACTED]
 
[REDACTED]
 
[REDACTED]
 
[REDACTED]
 
[REDACTED]
 
[REDACTED]
 
[REDACTED]

	
[REDACTED]
 
[REDACTED]
 
[REDACTED]
 
[REDACTED]
 
[REDACTED]
	
[REDACTED]
 
[REDACTED]
 
[REDACTED]
 
[REDACTED]
 
[REDACTED]
 
[REDACTED]
 
[REDACTED]
 
[REDACTED]
 
[REDACTED]
 
[REDACTED]
 
[REDACTED]

	
[REDACTED]
 
[REDACTED]
 
[REDACTED]
 
[REDACTED]
 
[REDACTED]
 
[REDACTED]
 
[REDACTED]
 
[REDACTED]
	
[REDACTED]
 
[REDACTED]
 
[REDACTED]
 
[REDACTED]

	
[REDACTED]
 
[REDACTED]
 
[REDACTED]
 
[REDACTED]
 
[REDACTED]
 
[REDACTED]
	
[REDACTED]
 
[REDACTED]
 
[REDACTED]
 
[REDACTED]
 
[REDACTED]
 
[REDACTED]
 
[REDACTED]
 
[REDACTED]
 
[REDACTED]

	Objectives	Endpoints
Safety	To evaluate the safety and tolerability of setmelanotide in patients with genetic variants in the MC4R pathway	Safety and tolerability assessed by the frequency and severity of AEs, changes in vital signs, and changes in laboratory evaluations at the end of Stage 1 and Stage 2

A. Estimand

Attribute	Description
Treatment	Setmelanotide
Population	Patients between ages of 6 and 65 with Specific Gene Variants in the Melanocortin-4 Receptor Pathway
Endpoint	Achieving a $\geq 5\%$ reduction in BMI from Baseline at the end of Stage 1
Intercurrent Events	For Discontinuation of randomized treatment or use of a rescue medication if any, Treatment policy strategy will be implemented.
Population-level Summary	Proportion of patients achieving a $\geq 5\%$ reduction in BMI from Baseline at the end of Stage 1

III. Study Design

A. Design Overview

This is a 2-stage (open-label stage followed by a randomized double-blind, placebo-controlled stage) Phase 2 trial of setmelanotide in patients with obesity with specific gene variants in the MC4R pathway. Approximately 100 patients between the ages of 6 and 65 years, inclusive, are planned to be enrolled in Stage 2 of the trial with up to 200 patients enrolled in Stage 1 (open-label).

Stage 1 (Open Label)

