All patients who are screened (including screen failed).

- **Safety Analysis Set**

All patients who received at least one dose of trial medication.

- **Safety Analysis Set Enrolled in Stage 2**

All patients from Safety Analysis Set who enrolled in stage 2 and received at least one dose of trial medication in stage 2.

- **Full Analysis Set (FAS)**

All patients randomized in Stage 2 who received at least one dose of trial medication (placebo or setmelanotide) after randomization in Stage 2 and have baseline weight data. Analyses performed on the FAS will be based on patients as randomized.

- **Supplemental Analysis Set (SAS)**

All patients who are eligible after the re-confirmatory genetic diagnosis.

M. Special Distribution Schedule

Hunger Questions and [REDACTED] will be recorded as:

Stage 1

Daily [Scenario 1] during the Screening Period, [Scenario 2] for 7 consecutive dates after the enrollment visit, [Scenario 3] for 7 consecutive days starting at Study Days 28, 56, and 84, and [Scenario 4] up to 14 consecutive days starting at Study Day 98. These questionnaires should be completed prior to the morning meal (after an 8-hour fast) and prior to dosing in the morning. During the Screening Period, the patient must complete these questionnaires at least 4 of the 7 days prior to V1 (enrollment visit). If a patient completes V7 (Week 16), and is not continuing into Stage 2 of the trial, the patient will stop completing these questionnaires after completing V7 (and return the electronic diary, if applicable).

Stage 2

[Scenario 2] for 7 consecutive days starting at Study Days 140, 168, 196, 224, and 252, and [Scenario 4] up to 14 consecutive days starting at Study Day 266 (Week 38). These

questionnaires should be completed prior to the morning meal (after an 8-hour fast) and prior to dosing in the morning. All patients will stop completing these questionnaires after Visit 14 (Study Day 280), regardless of whether they have completed the full 14 days of data entry (and return the e-diary, if applicable) or at their Early Termination Visit (if applicable).

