Medical history will be coded using Medical Dictionary for Regulatory Activities (MedDRA) version 24.1 Medical history will be tabulated by system organ class and preferred term. A listing of medical history will be provided.

VII. Efficacy Analyses

The analysis of the efficacy endpoints in Stage 1 will be performed based on the safety analysis set, and the analyses of the efficacy endpoints in Stage 2 will be performed based on the full analysis set (FAS). End of Stage 1 in below section will refer to the measurement collected at Week 16 and end of Stage 2 will refer to Week 40, unless otherwise specified. The tabulation and listing formats for all analyses below will follow section V.N unless otherwise specified.

A. Efficacy Assessments

A.1 Weight

Weight should be measured after patients have attempted to empty their bladders and after fasting for at least 8 hours. Patients are to wear light clothing or underwear and no shoes, with empty pockets and will be weighed at approximately the same time of day. All measurements will be recorded to the nearest 10th of a kg if reported with a digital scale, or half kg with a mechanical scale. Weight measurements will be collected in triplicate. Only in-person visits measurements will be summarized in tables.

[REDACTED]

[REDACTED]

[REDACTED]

[REDACTED]

[REDACTED]

[REDACTED] (Confidential) [REDACTED] [REDACTED]

[REDACTED]
[REDACTED]
[REDACTED]

[REDACTED]
[REDACTED]
[REDACTED]

[REDACTED]
[REDACTED]

[REDACTED]
[REDACTED]

[REDACTED]
[REDACTED]

[REDACTED]
[REDACTED]
[REDACTED]
[REDACTED]

[REDACTED]
[REDACTED]

[REDACTED]
[REDACTED]
[REDACTED]
[REDACTED]

[REDACTED]
[REDACTED]
[REDACTED]
[REDACTED]

[REDACTED]
[REDACTED]
[REDACTED]
[REDACTED]

[REDACTED]
[REDACTED]

[REDACTED]

[REDACTED]

[REDACTED]

VIII. Questionnaires

All patients in safety analysis set will be used for below analyses in Stage 1 and FAS in Stage 2 unless otherwise specified. The tabulation and listing formats for all analyses below will follow section V.N unless otherwise specified.

[REDACTED]

[REDACTED]

[REDACTED]

[REDACTED]

[REDACTED]

[REDACTED]

[REDACTED]

[REDACTED]

[REDACTED]

[REDACTED]

[REDACTED]

[REDACTED]

[REDACTED]

[REDACTED]

[REDACTED]

[REDACTED]

[REDACTED]

[REDACTED]

[REDACTED]

[REDACTED]

[REDACTED]

[REDACTED]

[REDACTED]

[REDACTED]

[REDACTED]

[REDACTED]

[REDACTED]

[REDACTED] (Confidential) [REDACTED] [REDACTED]

[REDACTED]
[REDACTED]
[REDACTED]
[REDACTED]
[REDACTED]

[REDACTED]

[REDACTED]

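### In single-arm Stage 1, treatment policy for an undefined rescue medication lets a 5% BMI reduction reached after adding another weight-lowering drug count as a response to setmelanotide

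*SAP*

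**What the plan says.** The estimand table in SAP II.A names setmelanotide alone as the treatment. Its intercurrent-event row covers stopping randomized treatment as well as rescue, and ends "use of a rescue medication if any, Treatment policy strategy will be implemented". The endpoint is a BMI reduction of at least 5% at the end of Stage 1, and Protocol Table 3 and Section 10.3 describe it as a response to setmelanotide.

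Stage 1 has no comparator. Protocol 7.2.1 states: "Stage 1 of the trial is open-label, and all patients will receive setmelanotide". SAP VII states: "The analysis of the efficacy endpoints in Stage 1 will be performed based on the safety analysis set". SAP V.L defines that set as "All patients who received at least one dose of trial medication".

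Other weight-lowering drugs are permitted as stable background. Protocol 7.7 says "GLP-1 receptor agonists and anti-obesity medications may be used as long as" three conditions hold, the last being that "the patient intends to keep the regimen and/or dose stable throughout the course of the trial". The same section expects all concomitant doses to stay stable unless an adverse event requires a change. It allows new medication that the treating physician judges necessary, after discussion with the Medical Monitor.

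Two visible rules turn a patient into a non-responder. SAP V.E does so when there is still no Week 16 BMI after the visit-window mapping. Protocol 6.3 does so when the patient stops trial medication. Neither mentions another weight-lowering treatment.

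**The concern.** Treatment policy uses the Week 16 BMI whatever happened before it. In a randomised comparison that gives a contrast between arms in which added treatment can occur on both sides. In a single arm there is no contrast, so any weight lost to a second drug goes directly into the proportion reported as response to setmelanotide.

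The row does not look written for this endpoint. It refers to discontinuing randomized treatment, although nobody is randomized until Day 112, and it names rescue without saying what would count as rescue in Stage 1.

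The stake is mainly the small-cohort results. Protocol 5.1.4 aims for up to 10 patients per gene. SAP V.N tabulates Stage 1 overall, by gene cohort and for each gene in the SEMA3 cohort, so one patient can visibly change how a gene looks.

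**Working it through.** The plan gives no figure to reproduce: SAP III.C says the sample size has no statistical basis, and neither document gives a rate of added weight-lowering treatment. The check is therefore a reading of the rules followed by an illustration.

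**Does any rule remove or recode the patient?** Take a patient who stays on setmelanotide, starts or increases another weight-lowering drug in Stage 1, and has a Week 16 BMI at least 5% below baseline.

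- SAP II.A: if the drug is rescue, treatment policy keeps the value and the patient is a responder. If it is not rescue, the row is silent and the value is still used.
- SAP V.E: does not apply, because the BMI is present.
- Protocol 6.3: does not apply, because trial medication continues.
- SAP V.L: the safety analysis set needs only one dose. The Supplemental Analysis Set is defined by genetics.
- SAP VI.C: protocol deviations are classified and listed, with no consequence for the endpoint.

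The patient is a responder on either reading of rescue.

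**Effect in one cohort.** Compared with a composite rule, each such responder adds 1/n. With n = 10 and the exact (Clopper-Pearson) interval of Protocol 10.3:

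| Count | Rate | Exact 95% CI |
|---|---|---|
| 3/10 | 30.0% | 6.7% to 65.2% |
| 4/10 | 40.0% | 12.2% to 73.8% |

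**Chance of at least one event among 10 patients**, 1 − (1 − c)^10, for assumed event rates c: 18% at c = 2%, 40% at 5%, 57% at 8%. Not every such patient will be a responder.

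**Pooled inflation.** Let p be the true setmelanotide response rate, c the share with the event, and r the chance that a patient with the event who would not otherwise respond reaches 5%. Assume the event is unrelated to whether the patient would have responded on setmelanotide alone.

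- Treatment policy minus truth = (1 − p) × c × r
- p = 0.30, r = 0.5, c = 0.02: 0.70 × 0.02 × 0.5 = 0.007, or 0.7 points
- p = 0.30, r = 0.5, c = 0.08: 0.70 × 0.08 × 0.5 = 0.028, or 2.8 points

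**Cost of the composite rule on the same assumptions.** It fails patients who would have responded anyway.

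- Truth minus composite = p × c
- c = 0.02: 0.30 × 0.02 = 0.6 points; c = 0.08: 0.30 × 0.08 = 2.4 points

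For a true rate of 30%, treatment policy would report 30.7–32.8% and the composite 27.6–29.4%. The two results bracket the truth.

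**The case against.** The best case for leaving the row alone has four parts.

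- **Rescue is undefined, and the SAP adds the qualifier that there may be none.** No Stage 1 rescue is described. The nearest provision is open-label setmelanotide after a BMI rise in Stage 2, which comes after this endpoint. A reader might infer that the SAP knowingly assigns added weight-loss drugs, or even bariatric procedures, to treatment policy. The text does not support that: applying the row to an added drug is an interpretation, and a procedure is not medication. The scoring result stands, because nothing else recodes the patient.
- **Conduct rules make the event uncommon.** This is fair. Protocol 7.7 restricts changes, Protocol 6.3 lets the investigator withdraw non-adherent patients, and SAP IX.G and IX.H tabulate or list concomitant medications and procedures. The events would be visible, but the primary proportion would not change.
- **The bias is not one-directional in every sense.** A reader might infer that the current rule can only overstate the response rate. That holds only relative to the composite rule. The composite itself would fail a patient who had passed 5% on setmelanotide before another drug was changed, for instance because of an adverse event. Likewise, multiplying 2–8% by one half gives 1–4 points, but that counts reclassified responders, some of whom would have responded anyway. It is not the inflation.
- **Little hangs on it formally.** SAP V.K plans no testing, and no success threshold is visible. The two intervals above overlap almost entirely. Stage 1 already mixes the drug effect with diet and activity counselling (Protocol 6.5). SEMA3 pools 13 genes and Other pools 14, so some reported cohorts may exceed 10 patients. This limits the weight of the point without removing it.

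Much of SAP VII is redacted. A sensitivity analysis for other weight-loss drugs may exist there, but it would not change the primary estimand in II.A.

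**Conclusion.** The concern holds in a limited form. As written, the primary estimand credits setmelanotide with a 5% BMI reduction reached after another weight-lowering drug was started or increased, and Stage 1 has no control arm against which to judge that contribution. The scoring follows from the visible rules and does not depend on how rescue is read.

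The size is modest. Each such responder is worth 10 points in a cohort of 10. Across the trial the inflation is about 0.7–2.8 points, which rests wholly on the assumed p, c and r because the documents supply none of them. The effect falls mainly on descriptive estimates in small gene cohorts. The change is worth making because it is cheap and fits the protocol's existing treatment of patients who stop therapy. The point does not show that the trial's overall conclusion is unsafe.

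**What to change.** In SAP II.A:

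1. Replace the rescue wording with a defined Stage 1 intercurrent event: starting, or increasing the dose of, another weight-lowering drug before the Week 16 measurement. Take the drugs from a list fixed before database lock, and before the Stage 1 interim analysis of SAP V.J if that comes first.
2. Add a bariatric procedure before Week 16 as a separate event, since the current row does not cover it.
3. Use a composite strategy for both in the primary analysis, so that a patient with either event is a non-responder.
4. Report the treatment-policy result as a sensitivity analysis, overall and by cohort, with the number of patients reclassified.

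Stopping setmelanotide is a separate matter: SAP II.A applies treatment policy and Protocol 6.3 counts a non-responder. Those passages must be reconciled while the row is open.

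**Cost.** One estimand row, a drug list and a flag. Concomitant medication is reviewed at every Stage 1 visit in Protocol Table 1, and procedures are already listed under SAP IX.H, so no new data are needed. Protocol Section 10 requires an amendment for a major change to the primary endpoint or its analysis, so the sponsor must decide whether this qualifies. The primary rate may be slightly conservative, because a patient already past 5% on setmelanotide before the change is counted as a failure. The sensitivity analysis shows by how much.

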Assessment	Stage 2 Entry Visit [†] (In-Person)	Virtual Trial Visits	In-Person Clinic Visits	End of Treatment Visit (In-Person)	End-of-Study Visit (Telephone) ²²	Early Termination Visit (In-Person)	Bridging Visits (if needed) (In-Person)
Visit Number	V7	V8, V9, V11, V13	V10, V12	V14	V15		
Study Week	16	18, 20, 28, 36	24, 32	40	44		Q12 weeks
Study Day	112	126, 140, 196, 252	168, 224	280			
Window (1)		+/-3	+/- 5	+/- 5	+/-3		+/- 5
Nutrition and physical activity counseling and follow-up	X	X	X	X			X
Physical Exam (2)	X			X	X	X	X
Comprehensive Skin Exam (3)	X			X	X	X	X
[REDACTED]							
[REDACTED]							
[REDACTED]							
Vital Signs (7)	X	X	X	X		X	X
ECG (8)	X			X		X	X
Pregnancy (9)	X	X	X	X		X	X
[REDACTED]							
[REDACTED]							
[REDACTED]							
C-SSRS (14)	X	X	X	X	X	X	X
PHQ-9 (21)	X	X	X	X	X	X	X
CDI-2 (23)	X	X	X	X	X	X	X

Table 2: Schedule of Assessments – Stage 2

Assessment	Stage 2 Entry Visit [†] (In-Person)	Virtual Trial Visits	In-Person Clinic Visits	End of Treatment Visit (In-Person)	End-of-Study Visit (Telephone) ²²	Early Termination Visit (In-Person)	Bridging Visits (if needed) (In-Person)
Visit Number	V7	V8, V9, V11, V13	V10, V12	V14	V15		
Study Week	16	18, 20, 28, 36	24, 32	40	44		Q12 weeks
Study Day	112	126, 140, 196, 252	168, 224	280			
Window (1)		+/-3	+/- 5	+/- 5	+/-3		+/- 5
[REDACTED]							
Randomization	X						
[REDACTED]	[REDACTED]						
Adverse events	X	X	X	X	X	X	X
Injection site inspection	X	X	X	X		X	X
Concomitant medication Review	X	X	X	X	X	X	X
Safety Laboratory Tests (15)	X		X	X		X	X
[REDACTED]							
[REDACTED]							
Trough PK (16)	X		X	X		X	X
Anti-Drug Antibodies (17)	X			X		X	X
Biomarkers (18)	X			X		X	X
Daily drug compliance (19)	X	X	X	X			X
Dispense/Return Trial medication (20)	X		X	X		X	X

Abbreviations: ADA = anti-drug antibodies; CDI-2 = Children’s Depression Inventory -2; C-SSRS = Columbia Suicide Severity Rating Scale; ECG = electrocardiogram; EOS = end of study; EOT = end of treatment; [REDACTED]; [REDACTED]; [REDACTED] PHQ-9 = Patient Health Questionnaire-9; PK = pharmacokinetic; Q = every.

† The Stage 2 Entry visit is the same visit as the final visit from Stage 1.

NOTE: Additional assessments may be performed at the Investigator’s discretion as needed to ensure patient safety.

¹ For patients who qualify for Stage 2 at the Week 16 visit in Stage 1, the Stage 2 Baseline Visit (B1) is the same as Week 16 in Stage 1.

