5.1.3.2. Switch to Treatment with Setmelanotide

During Stage 2 of the trial, patient weight will be monitored as per the SoA Stage 2 (Table 2). Additional virtual visits may be scheduled at the discretion of the Investigator.

Regardless of treatment assignment, patients will be offered to start open-label treatment with setmelanotide if, during a visit, a patient's BMI has increased by at least 5% from the Stage 2 entry weight measurement. Open-label treatment will be offered via enrollment in a separate LTE trial or, if the LTE trial is not available, via bridging visits until the LTE trial is available.

To be eligible, the patient must be scheduled for an in-person visit at the clinic. At the visit, the patient's body weight will be recorded. If the visit occurs within 2 weeks of an expected trial visit as per the SoA Stage 2 (Table 2), then the visit may replace that expected trial visit. All procedures as outlined in the SoA Stage 2 for the expected trial visit should occur. At this visit, the patient will return their double-blind trial medication supply. The patient may then be enrolled into the LTE trial or will be issued open-label setmelanotide and will continue in the trial via bridging visits until the LTE trial is available. The patient's initial assignment to either trial medication or placebo will continue to be blinded to all parties.

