The EOT Visit will occur as an in-person clinic visit on Study Day 112 for patients who complete only Stage 1 or on Study Day 280, which is the final day of treatment with setmelanotide or placebo for patients who complete Stage 2. A final End of Study (EOS) Visit will occur 4 weeks after the EOT visit. The EOS Visit will be conducted via telephone. At the end of Stage 2, patients may be offered the option of enrolling into a long-term extension (LTE) trial. If required by local regulation or if deemed necessary to assess patient safety by physical examination or after a longer follow-up period, the EOS Visit may be converted to an in-person visit, and/or can occur up to Week 48.

Regardless of treatment assignment, patients will be offered to start open-label treatment with setmelanotide if, during a visit, a patient's BMI has increased by at least 5% from the Stage 2 Entry Weight. Open-label treatment will be offered via enrollment in a separate LTE trial or, if the LTE trial is not available, via bridging visits until the LTE trial is available.

B. Study Population

Approximately 100 patients between the ages of 6 and 65 years, inclusive, are planned to be enrolled in Stage 2 of the trial with up to 200 patients enrolled in Stage 1 (open-label).

C. Sample Size Determination

Sample size is not based on any statistical considerations.

D. Treatment Randomization

At the Stage 2 Entry Visit, all eligible patients will be randomized 2:1 to either continue daily setmelanotide or receive matching placebo. Stratification by gene cohort will occur for specific genes being enrolled into this trial as determined by the Sponsor.

Patients with genetic variants in the following genes that have been categorized by a Clinical Laboratory Improvement Amendment (CLIA)/College of American Pathologists (CAP)/ISO15189 certified laboratory using American College of Medical Genetics (ACMG) criteria as (1) pathogenic, (2) likely pathogenic, or (3) a variant of uncertain significance as potentially causing dysfunction in the melanocortin-4 receptor pathway and leading to obesity are eligible for this trial. The genes eligible for enrollments are as following:

LEP, ISL1, DNMT3A, TRPC5, PLXNA4, NRP1, SEMA3E, SEMA3F, MECP2, SEMA3A, SEMA3C, PHIP, NRP2, MRAP2, MC3R, CPE, SEMA3B, SEMA3D, SIM1, HTR2C, SEMA3G, KSR2, MAGEL2, RPGRIP1L, TBX3, PLXNA1, CREBBP, PLXNA3, PLXNA2, TUB and OTHER.

E. Assessment Schedule

Refer to Appendix XII.

IV. Interventions

A. Treatment Administration

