In general, unless otherwise specified, events or measurements happen before the randomization date are in Stage 1 and happen on or after the randomization date are in Stage 2. For patients who are not randomized, all events or measurements are in Stage 1. All events happening after visit 14 will not be considered as in Stage 2 for patients who enrolled into bridging visit unless otherwise specified.

D. Definition of Baseline

Baseline Definition

Baseline will be defined as the last non-missing measurement taken prior to the start of stage 1 open-label treatment administration. In the case where the last non-missing measurement and the reference start date coincide and time of measurement is not available, that measurement will be considered Baseline unless the assessment was scheduled to be post-study drug administration in the SOA. Change from baseline is defined as the post-baseline value minus the baseline value, unless specified otherwise. Percent change from baseline = $(\text{Change from Baseline}/\text{Baseline}) \times 100$.

Study Day

Study Day will be calculated from the reference start date within stage and will be used to show start/stop day of assessments and events. Reference start date is defined as the day of first dose (Day 1) in stage1.

Study Day will be computed as follows:

(Confidential)

- Study Day = (date of event - date of first dose in stage 1) + 1 if the date of the event is on or after the date of first dose.
- Study Day = (date of event - date of first dose in stage 1) if the date of the event is prior to the date of first dose.

E. Missing Data

Unless stated otherwise, missing data will not be replaced with imputed values. When relevant, sections below will address how missing data will be handled for the particular analyses.

Analysis Window

All measurements recorded at unscheduled or early termination visits will be mapped according to the windowed visits by actual study day. These records then will be used for analysis if the scheduled ones are missing. If more than one visit occurs within a single visit window, then the analysis will take the one closest to and before the target day. All scheduled assessments will be analyzed according to the protocol defined visits, regardless of the study day

Stage	Study Visit	Study Week	Study Day	Study Day Window
1	Enrollment Visit	1	1	1
1	Virtual Visit 2	2	14	Post-dose - 21
1	Virtual Visit 3	4	28	22 - 35
1	Virtual Visit 4	6	42	36 - 49
1	Visit 5	8	56	50 - 70

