Low/Normal/High shift from baseline tables within stage will also be provided for hematology, coagulation and clinical chemistry. Normal/Abnormal shift from baseline tables within stage will also be provided for urinalysis.

Laboratory test results will be presented in data listings.

Pregnancy test will be presented in data listings.

E. Vital Signs

Vital signs include systolic and diastolic blood pressure (mmHg), heart rate (beats/min), respiration rate (breaths/min), and body temperature (°C). Vital signs will be obtained in the sitting position following at least 5 minutes of rest at each time point designated in the SOA.

All blood pressure and heart rate measurements will be taken in triplicate, approximately 2 minutes apart. The average of triplicate measurements will first be calculated within each patient then used in the summary statistics.

Summary statistics for actual values and changes from baseline within stage will be presented. Only in-person visits measurements will be summarized in table.

Vital sign data will also be presented in listing.

F. Physical Examination

Tanner staging data will be presented in listing.

G. Prior and Concomitant Medications

Prior and concomitant medications (CMs) will be coded using WHO-DD version September 2021.

G.1 Prior Medications

Prior medications are defined as medications with an end date prior to the first dose of study drug in Stage 1. Prior medications will be tabulated by Anatomic Therapeutic Chemical (ATC) Level 2 classification and Preferred Term (PT) by treatment group and overall. A patient having more than one medication within the same ATC Level 2 or preferred term will be counted only once for that ATC Level 2 or preferred term.

G.2 Concomitant Medications

Concomitant medications are defined as medications which are taken during the course of study stage. A detailed definition will be as following:

Stage 1

A medication will be considered a concomitant medication in Stage 1 as following:

- If the end date is completely missing and the medication start date is before the Stage 2.
- Or the medication start date is before the Stage 2 treatment administration and end date is on or after Stage 1 treatment administration or it is ongoing.

Stage 2

A medication will be considered a concomitant medication in Stage 2 as following:

- If the end date is completely missing
- Or the medication is either ongoing or end date is on or after Stage 2 treatment administration.

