- Any medications happening after the dosing date at visit 14 will not be considered as concomitant medication in stage 2

Concomitant medications will be tabulated by ATC Level 2 classification and PT by stage. A patient having more than one medication within the same ATC Level 2 or preferred term will be counted only once for that ATC Level 2 or preferred term.

A listing of prior and concomitant medications will be provided.

H. Concomitant Procedures

Concomitant procedures data will be listed by stage. The definition of stage will follow adverse events in IX.B.

I. Skin Examination

A comprehensive skin examination will be performed by the Investigator at the time points designated in the SOA.

The skin examination should include a full body (head-to-toe skin examination).

Frequency count of most severe outcome across all skin regions within patients will - be provided by stage and visit. The severity of the outcome is rated as Abnormal, CS > Anormal, Not CS > Normal > Not Done.

Also, the frequency count by skin region with abnormal result will be provided.

All skin examination data will be presented in listing.

J. Hyperpigmentation

Hyperpigmentation form will be administered at postbaseline visits.

All hyperpigmentation data will be presented in listing.

K. Sexual Function

Sexual function forms have different versions between male and female. All sexual function data will be presented in listing by version.

L. Electrocardiogram

A single 12-lead electrocardiogram (ECG) is performed at the visits designated in the SOA.

ECG measurements include PR interval (msec), RR interval (msec), QRS interval (msec), QT uncorrected (msec), QT corrected with Bazett's formula (msec), QT corrected with Fridericia formula (msec). Summaries of actual values and changes from baseline of these measurements will be presented.

A frequency and percentage table of normal, abnormal not clinically significant and abnormal clinically significant for overall ECG evaluation will be tabulated.

ECG data will be presented in listing.

M. Columbia-Suicide Severity Rating Scale (C-SSRS)

The C-SSRS that will be administered to patients ≥ 6 years of age according to the SOA.

There are two versions of the C-SSRS forms:

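### SAP V.C and IX.G.2 end Stage 2 for bridging patients only at Visit 14, so concomitant medications and listing records after an earlier switch to open-label setmelanotide stay in Stage 2

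*SAP*

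**What the plan says.** **Stage rule.** SAP V.C (Study Stage) places events and measurements before the randomization date in Stage 1, and those on or after it in Stage 2. The only upper limit for bridging patients is "All events happening after visit 14 will not be considered as in Stage 2 for patients who enrolled into bridging visit", subject to anything specified elsewhere.

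**Concomitant medications.** SAP IX.G.2 counts a medication in Stage 2 if its end date is completely missing, if it is ongoing, or if it ended on or after Stage 2 dosing began. The upper limit is again Visit 14: "Any medications happening after the dosing date at visit 14 will not be considered as concomitant medication in stage 2".

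**Switch route.** Under Protocol 5.1.3.2 a patient in either arm may be offered open-label setmelanotide once BMI has risen by at least 5% from Stage 2 entry. The patient returns the blinded supply and either enters the LTE trial or "will be issued open-label setmelanotide and will continue in the trial via bridging visits until the LTE trial is available". SAP III.A repeats the route: "if the LTE trial is not available, via bridging visits until the LTE trial is available". If the switch visit falls within 2 weeks of a scheduled visit, "then the visit may replace that expected trial visit".

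**Display.** Under SAP V.N, listings are ordered by gene cohort, stage and then treatment, and Stage 2 tables are split by treatment. The only treatment groups are active and placebo. The Stage 2 safety set in V.L carries no as-treated rule.

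**The concern.** Stage 2 is the only placebo-controlled part of the trial. A patient randomized to placebo who switches early is on setmelanotide from that day, but nothing readable in the SAP closes Stage 2 on that day. The effect is one-sided. An active patient who switches is still on setmelanotide, so the label stays true. A placebo patient's later records would describe open-label drug under a placebo label, and placebo would look more like active in the affected outputs.

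The readable rules appear to have only late bridging in mind. The disposition rule in SAP VI.B likewise covers only patients who finished Visit 14 and then moved to bridging visits. It says nothing about those who moved before.

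**Working it through.** The plan states no figure on this point. The check is to apply its rules to a placebo patient who switches early and remains on bridging visits.

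**Inputs**
- Randomization on Day 112 (Protocol 7.2.2).
- Visit 14 on Day 280. Visits 8 to 13 on Days 126, 140, 168, 196, 224 and 252 (Protocol Table 2).
- Replacement of a scheduled visit allowed within 2 weeks (Protocol 5.1.3.2).
- Bridging visits every 12 weeks (Protocol Table 2).
- About 100 patients in Stage 2, allocated 2:1 (SAP III.A and III.D).

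**Step 1: when the existing cut works.** If the switch visit replaces Visit 14, the Visit 14 cut and the switch coincide. The earliest such day is 280 − 14 = Day 266. All six scheduled visits between Stage 2 entry and Visit 14 (Days 126 to 252) fall before it.

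**Step 2: concomitant medications.** Take a switch on Day 168. A medication started after that day is ongoing, or ends after Stage 2 dosing began, so IX.G.2 counts it in Stage 2. It is removed only if it falls after dosing at Visit 14. If bridging visits replace the rest of the Stage 2 schedule, there is no Visit 14 and the exclusion has no date to act on. V.N then offers only active or placebo as the group.

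**Step 3: listings.** V.C gives the default stage label for records from bridging visits. With no readable rule ending Stage 2 at the switch, they are listed under Stage 2 and then under a treatment group.

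**Step 4: when bridging records arise.** Assume that the first bridging visit comes 84 days after the switch visit (12 × 7).

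| Switch day | First bridging visit |
|---|---|
| 126 | 210 |
| 140 | 224 |
| 168 | 252 |
| 196 | 280 |
| 224 | 308 |
| 252 | 336 |

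A second bridging visit would fall on Day 126 + 168 = 294 at the earliest. So there is at most one bridging visit per switcher by Day 280, and none by then for switches on Day 224 or 252. Without a Visit 14, the visits on Days 308 and 336 would also keep the Stage 2 label.

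**Step 5: safety tables.** Protocol Table 2 marks laboratory tests, skin examination and ECG in the bridging column. SAP IX.D, IX.I and IX.L each describe a table with no stated visit split: the laboratory shifts ("Low/Normal/High shift from baseline tables within stage will also be provided for hematology, coagulation and clinical chemistry"), the skin-region counts ("Also, the frequency count by skin region with abnormal result will be provided") and the overall ECG evaluation. If these tables pool all Stage 2 records, they would take in open-label records. If they are by visit, bridging records have no Visit 8 to 14 column to enter: bridging is its own schedule column and has no row in the SAP V.E window table. The text does not settle which applies.

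**Step 6: ceiling on numbers.** 100 × 1/3 ≈ 33 placebo patients. The documents give neither the share who would switch nor when, so no estimate below that ceiling is possible.

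**The case against.** The strongest objection concerns which outputs are touched. A reader might infer that the Stage 2 placebo columns for skin findings, ECG and laboratory shifts are contaminated. The documents do not establish that:
- SAP V.E says that scheduled assessments are analysed by protocol-defined visit.
- The neighbouring laboratory summaries and the first skin table are by stage and visit, and the shift and region tables are introduced as additions to them.
- Pooling would prove too much. V.C puts measurements on the randomization date in Stage 2, so a pooled table would already count every placebo patient's Visit 7 examination, made after 16 weeks on setmelanotide.
- An early switcher might have an early termination visit first. Protocol 5.2 asks for one from patients who discontinue before Day 280, but does not say whether a bridging switcher counts.

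This objection stands. Those three tables are ambiguous, not shown to be wrong.

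A reader might also extend the point to adverse events, concomitant procedures or Stage 2 efficacy. The stage definition for the first two is in IX.B, whose opening is not readable, and the Stage 2 efficacy text is blacked out. The opening of the safety section is not readable either, and V.C allows for rules specified elsewhere, so an as-treated or switch rule could be there. None appears in the readable medication, laboratory, skin or ECG text.

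On importance, the route needs a BMI rise of at least 5%, no available LTE trial and a switch before about Day 266. Protocol 7.7 asks for stable concomitant doses unless an adverse event requires a change, so few new medications are likely. Listings are patient-level, and study day lets a reader place a record in time. The blinded data review in SAP V.O could add the missing date. All of this lowers the importance, but none of it supplies a rule that ends Stage 2 at the switch.

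**Conclusion.** The Stage 2 end rule is incomplete. For a patient who switches before about Day 266 and stays in this trial, V.C and IX.G.2 as written keep open-label concomitant medications and default-rule listing records in Stage 2, with no cut date if Visit 14 never happens. Showing a placebo patient's records under placebo is an inference from the two display groups and the absence of a readable as-treated rule; the SAP does not state it.

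The point is minor. Its size is unknown, SAP V.K plans no statistical testing, patients who go straight to the LTE trial are not involved, and the primary endpoint belongs to Stage 1. The conclusion assumes that no blacked-out or otherwise unreadable text ends Stage 2 at the first open-label dose. The Day 210 to 336 dates assume 12-week spacing counted from the switch visit.

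**What to change.** State in SAP V.C and IX.G.2 that, for safety and concomitant-medication outputs, randomized Stage 2 ends at the earlier of Visit 14 and the first open-label setmelanotide dose. List or summarise later records separately by randomized arm, as an open-label bridging period and not under placebo. Report the number and timing of switches by arm. Say whether the laboratory shift, skin-region and overall ECG tables are by visit. Confirm that IX.B uses the same cut for adverse events, and so for concomitant procedures.

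The cost is SAP wording, one derived date and a little extra output. Switchers would contribute shorter Stage 2 safety follow-up. The criteria and procedure for switching are not changed.
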